		Note: within the glare PRO questionnaire, subjects are asked to compare their experiences with glare while using the study contact lenses against the lenses they wore just before starting the study. Please ensure that subjects understand that the comparator lens is the habitual brand of the contact lenses they were wearing prior to the study.	
6.6.	Entrance visual acuity	Record the entrance Snellen VA for each eye while wearing the study lenses.	
6.7.	Toric lens orientation	Record the toric lens orientation for each eye to the nearest degree.	
6.8.	Additional sample of toric lens orientation (1)	Instruct the subject to leave the consulting room and walk around for at least 2 minutes. Upon their return, measure and record the toric lens orientation to the nearest degree in each eye.	
6.9.	Additional sample of toric lens orientation (2)	Repeat the previous step once again.	
6.10.	Lens removal	Remove and place both lenses into a lens case with saline solution. Do not discard the lenses until after biomicroscopy has been completed.	

Visit 6: Follow-Up #4			
Step	Procedure	Details	
6.11.	Biomicroscopy	The FDA Slit Lamp Classification Scale will be used to grade findings. If any slit lamp finding is graded as 3 or worse, the subject must be discontinued, an adverse event will be recorded, and the subject will be monitored as per the guidelines given in section Error! Reference source not found Should the clearance of the fluorescein need to be expedited, preservative-free rewetting drops or artificial tears may be instilled. Study lenses may be discarded if there is no reason to store them following biomicroscopy.	

FINAL EVALUATION

The final evaluation will ordinarily take place immediately following the last scheduled follow-up visit per the study protocol. It may also take place at any point the subject discontinues the study or is terminated from the study.

	Final Evaluation				
Step	Procedure	Details			
F.1	Subject Disposition	Indicate if the subject completed the study successfully. If the subject is discontinued from the study, indicate the reason.			
F.2	Exit Refraction	Perform bare-eye subjective spherocylindrical refraction with a phoropter and record the best-corrected distance visual acuity (OD and OS) to the nearest letter. Note: This step is not necessary if the subject was			
	7	exited due to screen failure.			
F.3	Exit Slit Lamp Biomicroscopy (for subjects that are discontinued early)	FDA Slit Lamp Classification Scale will be used to grade the findings. If the clearance of the fluorescein needs to be expedited, preservative-free rewetting drops or saline may be instilled. This step is not necessary if the subject was exited due to screen failure.			
		Note: This step is not necessary if the subject was exited due to screen failure, or if biomicroscopy was performed as part of the final follow-up visit procedures (i.e., immediately prior to the final evaluation).			

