		Insufficient movement in all three movement			
		assessments (primary gaze, up-gaze and push-up test).			
		Excessive movement in primary gaze.			
		If the general fit is unacceptable for either eye, the			
		subject will be discontinued (proceed to exit			
		evaluation).			

		Visit 1: Lens Fitting #1	
Step	Procedure	Details	
			 
1.22.	Spherical over-refraction	Perform monocular spherical over-refraction using duo-chrome to refine the endpoint as described in step 1.11 (the final spherical endpoint may be determined binocularly).	
		The spherical over-refraction must be plano in both eyes to continue.	
		If a non-plano over-refraction is found in either eye, the lens(es) must be refit with the indicated change in sphere power. If the indicated lens power is not available for either eye (e.g., outside the available SKU range), the subject will be discontinued (proceed	
1.23.	Lens modification (if	to final evaluation). If modification is necessary in one or both eyes, select	g r
1.23.	necessary)	the reason for refitting lenses:	
		The settled lens rotation is such that a different cylinder axis would be more appropriate (use the LARS rule to determine the replacement lens cylinder axis) The spherical over-refraction is not plano Other (specify reason) Repeat steps 1.15 through 1.22 for one or both eyes, as appropriate.	
		A maximum of 2 lens modifications are allowed per eye. If, for either eye, the fit is not successful after 2 modifications, the subject will be discontinued (proceed to final evaluation).	
1.24.	Post-fit PRO questionnaire	Subjects will complete a PRO questionnaire regarding the initial comfort, vision and handling of the study lenses.	
1.25.	Additional sample of toric lens orientation (1)	Instruct the subject to leave the consulting room and walk around for at least 2 minutes. Upon their return, measure and record the toric lens orientation for each eye to the nearest degree.	
1.26.	Additional sample of toric lens orientation (2)	Repeat the previous step once again.	
1.27.	Exit visual acuity	Record the exit monocular distance Snellen visual acuity for each eye with the subject wearing the study lenses.	

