1.30.	Schedule next visit	Schedule the next visit to occur in 7(±2) days (counting the day of this visit as day 0, the subject may return on day 5 through 9). Ensure the subject is instructed to wear the study lenses for at least 1 hour immediately prior to attending the next visit.			

VISIT 2

Visit 2 will occur 5 to 9 days following Visit 1. Subjects must present to this visit wearing the study lenses in both eyes, and lenses must have been worn for at least 1 hour prior to the visit.

		Visit 2: Follow-Up #	1			
Step	Procedure	Details				
2.1.	Wear time and compliance	Record the subjects wearing time and comfortable wearing time. Subjects must have worn lenses for at least 8 hours on at least 5 days between the dispensing visit and this visit, and for at least 1 hour prior to attending this visit.				
2.2.	Review medical history and concomitant medications	Record any changes to the (including adverse events medications.				
2.3.	Subject reported ocular symptoms	Record any subject repor response to a verbal oper questionnaire.				
2.4.	Follow-up PRO questionnaire	Subjects will complete a PRO questionnaire to assess their experience with the study lenses. The glare PRO questionnaire will be completed first, followed by the CLUE questionnaire, followed by the other PRO items.				
2.5.	Entrance visual acuity	Record the entrance Snel wearing the study lenses.		ch eye while		
2.6.	Distance ETDRS visual acuity	Measure monocular discontrast (HLHC) visual 4 meters. Measure each eye using below:	acuity using E	TDRS charts	at	
		Condition	HI	HC		
		Room illumination	> 40	0 lux		
		Chart luminance	120 - 20	00 cd/m ²		
		Eye	OD	os		
		Charts	HC-1	HC-2		
2.7.	Toric lens orientation	Recorded letter-by-letter results into EDC. Record the toric lens orientation for each eye to the nearest degree.				
2.8.	Lens removal	Remove and place both lenses into a lens case with saline solution. Do not discard the lenses.				

Visit 2: Follow-Up #1			
Step	Procedure	Details	
2.9.	Biomicroscopy	The FDA Slit Lamp Classification Scale will be used to grade findings. If any slit lamp finding is graded as 3 or worse, the subject must be discontinued, an adverse event will be recorded, and the subject will be monitored as per the guidelines given in section Error! Reference source not found Should the clearance of the fluorescein need to be expedited, preservative-free rewetting drops or artificial tears may be instilled.	

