2.10.	Reinsert study lenses	The subject will reinsert the study lenses they removed prior to biomicroscopy.	
2.11.	Lens settling period	Following lens reinsertion, allow lenses to settle until, in both eyes: Reflex tearing has subsided The lens fit (centration and movement on blink) has stabilized The lens orientation has stabilized (orientation scribe mark has reached it's settled position)	
2.12.	Exit visual acuity	Record the exit monocular distance Snellen visual acuity for each eye with the subject wearing the study lenses.	
2.13.	Dispensing instructions	Provide the subject with additional study lenses (with the same lens code and power as dispensed earlier). • Minimum wear requirement: Instruct the subject to wear the study lenses for at least 8 hours per day (in a daily wear / daily disposable modality) on at least 5 days between the end of this visit and the start of the next visit. The day of the dispensing visit and/or the day of follow-up visit may be counted toward the 5 day requirement, but only if the study lenses are worn for at least 8 hours on those days. Note that, regardless of whether those days are counted toward meeting the minimum wear requirement, the return window requirement still holds (i.e., counting the day of this visit as day 0, the subject must still return for their next visit on day 5 through 9).	
		 Subjects must not wear their habitual lenses at any time during study lens wear periods (spectacle wear is acceptable on non-wearing days). Preservative-free rewetting drops are permitted, if needed. Ensure the subject has enough remaining study lenses to complete the wear period through to the next follow-up visit (if additional lenses are needed, complete an unscheduled visit for lens resupply). 	

	Visit 2: Follow-Up #1		
Step	Procedure	Details	
		Instruct the subject to bring their habitual spectacles or contact lenses to the next visit (to wear following removal of the study lenses).	
		Note: In the event that a subject requires additional lenses due to loss or damage, they may return to the clinical site for lens replacement. As much as reasonably possible, damaged lenses and packaging should be returned to the clinical site (in solution, if possible) for shipping to the Sponsor. If lens damage is present, complete the Product Quality Complaint Form, store the lens in a labeled vial with saline and return it to the Sponsor.	

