4.4.	Remove habitual lenses (if worn)	If worn, the subject's habitual contact lenses will be removed. Lenses may be stored in a lens case, if required.	
4.5.	Biomicroscopy	The FDA Slit Lamp Classification Scale will be used to grade findings. If any slit lamp finding is graded as 3 or worse, the subject must be discontinued, an adverse event will be recorded and the subject will be monitored as per the guidelines given in section Error! Reference source not found.	
		Should the clearance of the fluorescein need to be expedited, preservative free rewetting drops or artificial tears may be instilled.	
4.6.	Continuance	Verify that the subject is eligible to continue in the study.	V S

Visit 4: Lens Fitting #2

The steps followed will be the same as those listed under Visit 1: Lens Fitting #1.

VISIT 5

Visit 5 will occur 5 to 9 days following Visit 4. Subjects must present to this visit wearing the study lenses in both eyes, and lenses must have been worn for at least 1 hour prior to the visit.

Visit 5: Follow-Up #3

The steps followed will be the same as those listed under Visit 2: Follow-Up #1.

VISIT 6

Visit 6 will occur 5 to 9 days following Visit 5. Subjects must present to this visit wearing the study lenses in both eyes, and lenses must have been worn for at least 1 hour prior to the visit.

Subjects should bring their own habitual spectacles or contact lenses to this visit to wear following study lens removal.

Visit 6: Follow-Up #4			
Step	Procedure	Details	
6.1.	Wear time and compliance	Record the subjects wearing time and comfortable wearing time. Subjects must have worn lenses for at least 8 hours on at least 5 days during the dispensing period, and for at least 1 hour prior to attending this visit.	
6.2.	Collect unworn lenses	Collect any unworn study lenses that were dispensed at the previous visit.	
6.3.	Review medical history and concomitant medications	Record any changes to the subject's medical history (including adverse events) or concomitant medications.	
6.4.	Subject reported ocular symptoms	Record any subject reported ocular symptoms in response to a verbal open-ended symptoms questionnaire.	
6.5.	Follow-up PRO questionnaire	Subjects will complete a PRO questionnaire to assess their experience with the study lenses.	
		The glare PRO questionnaire will be completed first, followed by the CLUE questionnaire, then the other PRO items, then the preference questionnaire.	

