8.2. Withdrawal/Discontinuation from the Study

A subject will be withdrawn from the study for any of the following reasons:

- Subject withdrawal of consent.
- Subject not compliant to protocol.
- Subject lost to follow-up.
- Subject no longer meets eligibility criteria (e.g. the subject becomes pregnant).
- Subject develops significant or serious adverse events necessitating discontinuation of study lens wear.
- Subjects who have experienced a Corneal Infiltrative Event (CIE).
- Investigator's clinical judgment regarding the subject safety reasons (that it is in the best interest of the subject to stop treatment).
- Subject misses any study visits.
- Subject not compliant with study lens wear schedule.
- Subject not successfully dispensed due to lack of efficacy and safety including poor vision, poor comfort or unacceptable fit.

For discontinued subjects, the Investigator will:

- Complete the current visit (scheduled or unscheduled).
- Complete the Final Evaluation, indicating the reason that the subject was discontinued from the study.
- Record the spherocylindrical refraction with best corrected distance visual acuity.
- Collect used test article(s) (worn or brought to the visit) from the subject and discard them, unless otherwise stated in section 7.2.
- Collect all unused test article(s) from the subject.
- Make arrangements for subject care, if needed, due to their study participation.

Additional subjects may be enrolled if a subject discontinues from the study prematurely.

In cases where a subject is lost to follow-up, every possible effort must be made to contact the subject and determine the reason for discontinuation/withdrawal. The measures taken to follow up must be documented including two written attempts and a certified letter (or equivalent) as the final attempt.

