- Any active disease, injury, or abnormality affecting the comea, conjunctiva, or eyelids that may be exacerbated by contact lens wear
- Inadequate tear film (dry eye) that interferes with contact lens wear Reduced corneal sensitivity (corneal hypoesthesia)
- If eyes become red or irritated
- Use of any medication that is contraindicated or interferes with contact lens wear, including certain eye medications
- Any systemic disease which may be exacerbated by or interferes with safe contact lens wear, handling, or care
- Allergic reactions of the ocular surfaces or adnexa that may be caused by or exacerbated by the wearing of contact lenses
- Patient history of recurring eye or eyelid infections, adverse effects associated with contact lens wear, intolerance, or abnormal ocular response to contact lens

WARNINGS

Advise patients of the following warnings pertaining to contact lens wear:

- Problems with contact lenses and lens care products could result in serious injury to the eye. It is essential that patients follow their Eye Care Professionals directions and all labelling instructions for proper use of lenses and lens care products. Eye problems, including corneal ulcers, can develop rapidly and lead to loss of vision.
- It a patient experiences eye discomfort, foreign body sensation, excessive tearing, vision changes, or redness of the eye, the patient should be instructed to immediately remove lenses and promptly contact his or her Eye Care Professional. It is recommended that contact lens wearers see their Eye Care Professional regularly as directed.
- Studies have shown that contact lens wearers who smoke have a great suffering ulcerative keratitis than among those who are nonsmokers.
- Daily wear lenses are not indicated for overnight wear, and patients should be instructed not to wear lenses while sleeping. Clinical study results' have shown that the risk of ulcerative keratitis is greater for daily wear users who wear their

- lenses overnight (outside the approved indication) compared to those who do not wear them overnight.

 Non-sterile liquids (i.e., tap water, distilled water, homemade saline solution, or
- saliva) should not be used as a substitute for any component in the lens care process. The use of tap and distilled water has been associated with Acanthamoeba keratitis, a comeal infection that is resistant to treatment and

PRECAUTIONS

To prevent damage to the eyes or to the contact lenses, the following precautions should be taken:

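### At Visits 2 and 5 a Grade 3+ slit-lamp finding requires discontinuation, but no exit from the visit is stated, and the steps that follow conflict with sections 8.2 and 6.6

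*Combined protocol and SAP*

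**What the plan says.** Visits 2 and 5 are the 1-week follow-ups of the two lens periods. At Visit 2 the lenses are removed (step 2.8, with an instruction not to discard them) and the eye is examined. Step 2.9 then states: "If any slit lamp finding is graded as 3 or worse, the subject must be discontinued, an adverse event will be recorded". It names no next step, and its cross-reference to monitoring guidance does not resolve.

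Step 2.10 follows directly: "The subject will reinsert the study lenses they removed prior to biomicroscopy". Step 2.11 lets the lenses settle and step 2.12 takes exit acuity in them. Step 2.13 begins "Provide the subject with additional study lenses (with the same lens code and power as dispensed earlier" and continues with wear instructions up to the next visit, and step 2.14 schedules Visit 3. None of these steps excepts a subject just discontinued. For Visit 5 the protocol says only: "The steps followed will be the same as those listed under Visit 2: Follow-Up #1".

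Section 8.2 lists what the investigator does for a discontinued subject. The first item is "Complete the current visit (scheduled or unscheduled". Later items require the Final Evaluation, collection of used lenses (to be discarded unless section 7.2 states otherwise), and "Collect all unused test article(s) from the subject". Section 6.6 says that a lens associated with an adverse event must, when possible, be retained in a vial pending the sponsor's directions. The Final Evaluation text in section 7.2 allows that evaluation at any point at which a subject discontinues.

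**The concern.** A site that follows the numbered steps in order, or that takes the first item of section 8.2 literally, returns the lenses to an eye just graded moderate or severe and supplies more of them. A site that follows the rest of section 8.2 collects the lenses instead. Both can claim to be following the protocol.

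What is at stake is first the safety of the affected eye during that visit. The second matter is consistent handling across up to six sites: whether the lens goes back in, is discarded, or is kept for the sponsor depends on which passage the site reads.

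**Working it through.** No arithmetic applies, and no stated figure needs to be reproduced. The check sets the passages side by side.

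**Where the gap arises.** Table 3 marks lens reinsertion and settling only at Visits 2 and 5. Visits 3 and 6 have no reinsertion. Visit 4 carries the same Grade 3+ rule at step 4.5, but a continuance check (step 4.6) follows before any lens is fitted. The gap is therefore confined to 2 of the 4 follow-up visits, one in each lens period.

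**Literal trace for a subject with a Grade 3+ finding at Visit 2.**

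1. Step 2.9: discontinue the subject and record an adverse event. No exit is given.
2. Section 8.2, first item: complete the current visit. No step is excepted.
3. Steps 2.10 to 2.12: the removed lenses go back in, settle, and acuity is measured in them.
4. Steps 2.13 and 2.14: more lenses are supplied and Visit 3 is booked.
5. Section 8.2, later items: collect used lenses, collect all unused lenses, complete the Final Evaluation.

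Items 4 and 5 contradict each other directly. Nothing in the trace excludes item 3.

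**What happens to the lens removed at step 2.8.**

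| Passage | Destination of the removed lens |
|---|---|
| Step 2.8 | Kept in a case, not discarded |
| Step 2.10 | Back in the eye |
| Section 8.2 | Collected, and discarded unless section 7.2 says otherwise |
| Section 6.6 | Retained in a vial when possible, because step 2.9 makes this an adverse event |

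Step 2.8 may count as the exception that section 8.2 allows, but that would affect only the discarding and not the collection.

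**How the protocol drafts the same situation elsewhere.**

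- Step 1.12 (Grade 3+ at baseline) stops the visit itself. Step 2.9 stops the subject's participation, and section 8.2 then says to complete the visit.
- Steps 1.20, 1.22 and 1.23 send the discontinued subject to the final evaluation; step 1.23, for example, reads "the fit is not successful after 2 modifications, the subject will be discontinued (proceed to final evaluation". Steps 1.21 and 1.28 likewise name an exit evaluation.
- Step 1.29 makes dispensing conditional on the lenses being suitable. Step 2.13 has no such condition.

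The authors therefore state an exit or a condition at the Visit 1 gates and omit one at step 2.9.

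**A related tension.** Section 13.3 leaves continuation after an adverse event to the investigator's judgment, whereas step 2.9 makes discontinuation mandatory.

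**Bearing on the primary endpoint.** Section 2.2 fixes the primary endpoint at about 2 weeks of wear, and Visits 2 and 5 fall at 7±2 days. The grade is also recorded at step 2.9, before any reinsertion, so steps 2.10 to 2.14 cannot change it. Table 7 gives precision for 0, 1 or 2 events among 120 eyes on the 2-week measure and says nothing about how often the 1-week situation will occur.

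**The case against.** The strongest reply is that mandatory discontinuation plainly ends the sequence and that an experienced site would stop at step 2.9. Several passages support this:

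- The Final Evaluation may take place at any point of discontinuation, so an exit exists.
- Section 8.2 requires collection of both used and unused lenses, which is incompatible with sending the subject home to wear more.
- Section 6.3 limits dispensing to subjects who meet the eligibility and dispensing requirements.
- Section 13.1 lists other corneal findings of Grade 3 or higher among significant adverse events, a class defined as warranting temporary or permanent cessation of lens wear.
- The instruction to complete the visit also covers unscheduled visits, where most steps apply only as needed, so it need not mean every step.

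Much of this stands. A reader might infer that the protocol orders re-exposure of an affected eye. The documents do not support that, and continued wear at home is contradicted by section 8.2 itself.

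It does not remove the gap. The Final Evaluation text permits an early exit without requiring one. Section 6.3 concerns dispensing, not reinsertion during the visit. No passage says which steps of Visit 2 lapse, although the Visit 1 gates show that the authors knew how to say so.

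Two further inferences are tempting and should not be drawn. One is that the primary endpoint is distorted; the timing of the visits and the order of the steps rule that out. The other is that reinsertion undermines the causality assessment. Section 13.2.1 mentions de-challenge and re-challenge only as an example under one category, and otherwise relies on timing and alternative explanations. Exclusion criterion 11 and the Control lens insert add little, since the first applies at baseline and the second to one lens only.

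**Conclusion.** The point holds as a missing branch after step 2.9 and a contradiction among step 2.9, steps 2.10 to 2.14, section 8.2 and section 6.6. It recurs at Visit 5. The consequence is for patient safety and for consistent handling of lenses, not for estimation: no sample size, precision figure or primary result changes.

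Its reach is one visit per lens period for every subject, but it takes effect only when a Grade 3+ finding occurs at 1 week. The documents give no expected frequency for that, so none is claimed here. The conclusion assumes that sites work from the numbered steps and section 8.2 as written; many would stop at step 2.9 unprompted. It is worth correcting because the eyes concerned are the ones with moderate or severe findings and the correction is small.

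**What to change.** Reconcile the four places in a protocol revision:

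- After step 2.9, and so for Visit 5, state which of the remaining steps apply to a subject just discontinued, in the form used at the Visit 1 gates.
- In section 8.2, state which parts of the current visit are to be completed after discontinuation, so that this item and the lens-collection items can all be followed.
- In the same wording, say how section 6.6 on retaining lenses applies to the pair removed at step 2.8.

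Repair the broken cross-reference in step 2.9 and align it with section 13.3 in the same revision. Which steps apply, and what is done with the lenses, is clinical content for the sponsor's clinical team to set.

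The core change is about two sentences. It adds no visits, data or subjects.
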